STUDY PROTOCOL

Click Here to upgrade to Unlimited Pages and Expanded Features

GENERAL INFORMATION

Title	: Effect of maternal voice on physiological and behavioral measures in premature
	infants : A Randomized Controlled Trial
Protocol ID	18906
Investigator	: [name] [name] ([name])
Address	: Jabatan Pediatrik, Hospital Sultanah Bahiyah, [name]
Site of study	:NICU Hospital Sultanah Bahiyah, Alor Setar

LITERATURE REVIEW

Premature infants remains in an isolette, an enclosed incubator where touching and sensory stimulation are restricted. Research has shown that ambient auditory stimuli from the surrounding NICU environment occur frequently, spike unpredictably, and can have deleterious consequences for the neonate (Standley 2000).

The human fetus can perceive and react to auditory information starting at approximately week 26 of life(Ruben, 1991). A study by *(Graven, 2000⁾* recommended that noise levels should not exceed 50 to 55 dB in the NICU. However, researchers have reported that NICU sounds average between 50 and 90 dB (Levy et al., 2003)

It is well known that sound levels in the NICU are a major source of environmental stress for premature infants(Peng et al., 2013) Studies have indicated that increased noise levels are associated with increased fatigue, stress behaviors, hyperalerting responses, startle, hypoxemia, agitation, crying, sleep interruptions, and intracranial pressure in neonates (Standley, 1991) (Caine, 1991)

The most common indicators of physiological stress and pain are similar and include changes in heart rate, respiratory rate, blood pressure, transcutaneous oxygen levels (tcP02), oxygen saturation (O2 Sat), intracranial pressure, vagal tone, skin blood flow, and palmar sweat (Peng et

Click Here to upgrade to Unlimited Pages and Expanded Features ce supports the use of music in critical areas such as sucking 3ain(Kemper and Hamilton, 2008), sleep(Arnon et al., 2006),

and recovery from painful procedures (Tramo et al., 2011, Hartling et al., 2009) Vocal familiarity within the infant's sound environment may provide an essential domain of consistency, security, and comfort that even the most modern NICUs cannot replicate. Studies of mothers singing live, infant directed lullables to newborns indicate stabilizing effects(Shenfield et al., 2003). Parents' voices have also been shown to enhance vocalization in premature infants.(Shenfield et al., 2003)

Studies have shown that preterm infants who were exposed to an audio recording of their mother's voice achieved full enteral feed quicker and showed meaningful changes in heart rate compared to age-matched controls receiving routine care (Krueger et al., 2010)

OBJECTIVES AND PURPOSE

General

O To determine the effect of maternal voice vs NICU environmental sounds on physiological and behavioral measures in premature infants.

Specific

- O To compare mean changes of HR, RR,SPO2 in infants exposed to mother's voice vs NICU environmental sound.
- O To compare mean weight gain between premature infants exposed to mother's voice vs NICU environmental sound
- O To compare mean neurobehavioral score between premature infants exposed to mother's voice vs NICU environmental sound

Click Here to upgrade to Unlimited Pages and Expanded Features Study design

This study is a randomized control trial for premature infants from 27-35 weeks CGA who is admitted to NICU Hospital Sultanah Bahiyah, Alor Setar between June 2015 to November 2015.

Sample size

Based on previous study by (Alipour et al., 2013), the sample size to achieve a power of 0.8, alpha level of 0.05, and the mean difference of 5 with standard deviation of 9.57 for physiological responses was 58 per group is needed. Therefore, total sample size of 140 is needed with 20% drop out.

Inclusion Criteria

- 1. All premature infants with corrected gestational age 27-35 weeks
- 2. Achieved full feeding of at least 120cc/kg/day
- 3. Infant must be nursed in closed incubator (isolette)

Exclusion Criteria

- 4. Premature baby who are on mechanical ventilation
- 5. Medically unstable infant: HIE, NEC, sepsis, on inotropic support
- 6. Infant with major congenital anomalies
- 7. Infant who is still on intravenous drip or parenteral nutrition

Dropout criteria

- O Infant who need to be ventilated during study period
- O Infant who need to be kept nil by mouth during study period
- O Infant who become medically unstable determined by treating clinician: HIE, NEC, sepsis, on inotropes etc

Click Here to upgrade to Unlimited Pages and Expanded Features Study protocol:

All premature infants who fulfill the eligibility criteria of the study are identified. An appointment for a meeting with parents for consent will be arranged via phone or when parents visited the infant. The meeting will take place in NICU, Hospital Sultanah Bahiyah, Alor Setar. After consent is obtained, all infant's mother will be asked to sing appropriate lullaby of their choice due to multiracial population. The session will be recorded using a voice recorder (SONY ICD-UX543F) for 10 min in predetermine quiet room to minimize sound interference.

All subjects will be randomized into two groups that are Intervention and Control. All subjects are randomized into two groups by block randomization. Computer software is use for creation of randomization. Coding systems will be used instead of real name to identify each infant. All subject's data will be kept in a secured and separated cabinet locked in the departmental room of the investigator in Hospital Sultanah Bahiyah. An officer (Sister in charge of NICU) will be incharge of the list of subjects and all the equipments needed.

Intervention group will be receiving prerecorded maternal voice while control will have the same settings but without maternal voice recording.

All subject will be placed in own incubator. A neurobehavioral observation will be done using Behavioral Indicators of Infant Pain (BIIP) pre and post intervention (Holsti and Grunau, 2007). Infants belonging to the intervention group underwent daily sessions of exposure to maternal voice recorded in agreement with the American Academy of Pediatrics that recommends safe sound levels within the NICU 50-55dB. Sound level meter (Mini Digital Decibel Audio Sound Pressure Meter MTR01DASP) will be used to monitor and maintain sound between level 50-55db throughout intervention. The voice recorder will be placed 10cm from infant ear.

Intervention group will be exposed to total of 14 times (daily) prerecorded maternal voice within 2 week-period. Each session will last for 30 min that is 10 min pre intervention, 10 min during intervention, 10 min post intervention. Heart rate, respiratory rate and SPO2(physiological parameter) will be centrally monitored and recorded every minutes in each session. Physiological parameters will be recorded every minute while weight gain will be monitored every alternate day for 2 weeks using a standard weighing machine.

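### No primary outcome is named, and the difference of 5 with SD 9.57 is tied to no variable, unit or time point, so the stated 0.05 and 0.8 are justified for at most one unidentified outcome

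*Protocol*

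**What the plan says.** The Protocol's specific objectives (Objectives and purpose) cover five outcomes in three bullets. The first takes three variables together: "To compare mean changes of HR, RR,SPO2 in infants exposed to" the mother's voice or NICU sound. The second concerns weight gain. The third reads "To compare mean neurobehavioral score between premature infants exposed to" the same two conditions, and the instrument is the BIIP. No bullet is ranked above another, and no outcome is called primary anywhere in the document.

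The Sample size section, drawing on an earlier study of vocal stimulation in premature infants, gives "the sample size to achieve a power of 0.8, alpha level of 0.05" and continues: "and the mean difference of 5 with standard deviation of 9.57 for physiological responses was 58 per group is needed". No variable, unit or time point is attached to the 5 or the 9.57. The Study protocol section treats heart rate, respiratory rate and SpO2 together as the physiological parameter. They are recorded each minute through three 10-minute windows (before, during and after), in daily sessions, 14 in all.

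The Statistical analysis section plans one repeated-measures ANOVA for a dependent variable that it does not name.

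**The concern.** A difference and an SD in one unit can justify the power of one variable. Heart rate is counted in beats per minute, respiratory rate in breaths per minute and SpO2 in per cent, so a single unlabelled pair cannot be read as covering all three. The time window matters as well: the SD of a one-minute reading, of a 10-minute mean and of a mean over 14 sessions will generally differ.

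Two things are at stake. First, a null result on any outcome is hard to interpret, because the reader cannot tell whether the trial was sized for it. Second, with five outcomes listed as equals and no success rule, nothing in the text stops whichever outcome reaches 0.05 from being presented as the trial's finding. The error rate of that conclusion would not be 0.05.

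**Working it through.** **Inputs from the Protocol.** Difference 5, SD 9.57, power 0.8, alpha 0.05 (sidedness not stated), two groups, 58 per group (Sample size). Five outcomes (Objectives and purpose).

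**1. The plan's own figure.** With equal groups and a two-sided test,

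n = 2 × (1.960 + 0.842)² × (9.57/5)² = 2 × 7.849 × 3.663 = 57.5, rounded up to 58 per group.

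This matches. A one-sided test would give 46, so two-sided 0.05 was evidently used. The exact t-test needs 58.48, that is 59, which is a negligible difference. The standardised difference is 5/9.57 = 0.522, and power at 58 per group is Φ(0.522 × √29 − 1.960) = 0.803.

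**2. Which outcome can the pair describe?**
- *BIIP:* it cannot. The form's maximum is 2 (state) + 5 (face) + 2 (hand) = 9, so the SD of a score is at most 9/2 = 4.5. Even a change score, bounded by −9 and +9, has an SD of at most 9.
- *Weight gain:* the pair is given for physiological responses, so it is not offered for weight gain.
- *Heart rate, respiratory rate, SpO2:* the text does not distinguish between them.

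**3. What the power would be if the pair belongs elsewhere.** The alternative values are assumptions, because the documents give no other figures. Power at 58 per group, two-sided 0.05:

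| Difference | SD | Power |
|---|---|---|
| 5 | 9.57 | 0.80 |
| 5 | 12 | 0.61 |
| 5 | 15 | 0.43 |
| 5 | 20 | 0.27 |
| 3 | 9.57 | 0.39 |
| 2 | 9.57 | 0.20 |

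**4. Familywise error.** With five independent tests at 0.05: 1 − 0.95⁵ = 0.226. With three: 1 − 0.95³ = 0.143. The other rows come from simulating equally correlated normal test statistics (400,000 draws); the correlations are assumptions.

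| Common correlation | Five outcomes | Three physiological outcomes |
|---|---|---|
| 0 | 22.6% | 14.3% |
| 0.3 | 20.9% | 13.6% |
| 0.5 | 18.3% | 12.6% |
| 0.8 | 12.7% | 9.8% |

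**5. Price of keeping five equal outcomes.** Bonferroni gives 0.05/5 = 0.01 per test. If every outcome had the standardised difference 0.522 (an assumption the documents do not support), power at 58 per group would be Φ(0.522 × √29 − 2.576) = 0.59, and 80% power would need 86 per group.

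**The case against.** The strongest reply is that no stated figure is wrong. The 58 reproduces, and the source study may well have supplied the pair for one particular variable. The Sample size section also singles out physiological responses, so the five outcomes are not on a wholly equal footing. Weight gain and BIIP need no power calculation if they do not drive the sample size. The protocol sets no rule that any one significant result counts as success, and multiplicity adjustment may sit in an analysis plan that is not shown.

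Most of this stands, and it limits the point. The absence of an adjustment method is not an error here, and the familywise figures are conditional on any of the five tests being allowed to carry the claim. The reply does not remove the core. Choosing the primary outcome determines the sample size, and the sample size is stated in this document. Singling out physiological responses still leaves three candidates.

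A reader might also infer several stronger things that the documents do not support:
- *That 0.05 and 0.8 can be true of only one outcome.* Each unadjusted test keeps its own 0.05, and any outcome with a true standardised difference of about 0.52 or more would have 80% power. The text merely justifies these values for at most one outcome.
- *That an SD of 9.57 is impossible for SpO2.* The documents give no SpO2 mean or SD. At an assumed mean of 95%, a variable bounded by 0 and 100 can have an SD up to √(95 × 5) = 21.8, and the objective concerns changes, which are not capped at 100. Such an SD looks implausible in stable infants, but it is not excluded.
- *That testing the during and post windows separately doubles the tests to ten, with 40% familywise error.* Weight is taken every other day and has no such windows, so the most would be 4 × 2 + 1 = 9 tests, or 1 − 0.95⁹ = 37% under an independence that adjacent windows in the same infants would not satisfy. The protocol does not set out separate tests of this kind.

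**Conclusion.** The point holds in a limited form. The protocol names no primary outcome among five, and a correct sample size calculation is attached to no identifiable variable, unit or time point. Its 0.05 and 0.8 are therefore justified for at most one outcome, which a reader cannot identify.

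If any of five unadjusted tests may support the claim, the chance of at least one false positive lies between about 13% and 23%, for assumed common correlations from 0.8 down to 0. That range rests on the assumed correlations and on the absence of a success rule. The finding that the pair is unlabelled rests on the text alone. Because naming the primary outcome is a protocol decision bound to the stated sample size, an unseen analysis plan would not cure it.

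**What to change.** Before any data are analysed:

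1. State in the Sample size section which variable, unit and time window the 5 and 9.57 refer to.
2. Name that variable as the single primary outcome, tested at two-sided 0.05, and say that the 0.8 power applies to it only. The 58 per group then stands.
3. Label the other physiological variables, weight gain and BIIP as secondary, to be read as supportive and reported with confidence intervals.
4. If the investigators prefer a different primary outcome, for instance on grounds of clinical relevance, restate the power for that variable at 58 per group from its own difference and SD.

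If the pair's own variable is kept as primary, the cost is wording only, with no extra infants. With a different primary, the required number could change. In either case a lone significant secondary outcome can no longer be claimed as proof that maternal voice works.

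### Minor arithmetic error: a total of 140 with the stated 20% drop-out leaves 56 infants per group, not the 58 the protocol says it needs

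*Protocol*

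**What the plan says.** The Sample size section of the protocol takes its planning values from one earlier study. It sets the target as "the sample size to achieve a power of 0.8" with "alpha level of 0.05", and gives the effect, the spread and the result together: "the mean difference of 5 with standard deviation of 9.57 for physiological responses was 58 per group is needed". The next sentence moves from the evaluable number to the number to enrol: "Therefore, total sample size of 140 is needed with 20% drop out". No inflation formula is shown.

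The Dropout criteria that follow are need for ventilation, need to be kept nil by mouth, and medical instability arising while the infant is in the study. The Study protocol section adds "All subjects are randomized into two groups by block randomization", without stating the ratio. No other part of the protocol gives a different total or drop-out rate.

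**The concern.** The total is presented as following from 58 per group and a 20% drop-out allowance. Such an allowance is meant to ensure that the required number remains after the expected losses. A drop-out rate is ordinarily a share of the infants enrolled, and the protocol's own drop-out criteria apply to infants already in the study. On that reading 140 falls short of what the preceding sentence requires, so the size, the drop-out rate and the power cannot all hold together. This is the protocol's only sample-size statement, and an error in it is likely to be carried into the report of the trial.

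**Working it through.** **Inputs (Protocol, Sample size):** power 0.80; alpha 0.05; mean difference 5; SD 9.57; 58 per group; drop-out 20%; total 140.

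**Assumptions:** alpha is two-sided, which the protocol does not state but which reproduces 58 (one-sided gives 46). Allocation is 1:1, implied by the single per-group figure. Losses are equal in the two groups.

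**Step 1. Reproduce the base figure.** For two means by the normal approximation:

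n per group = 2 × (1.960 + 0.842)² × (9.57/5)² ≈ 57.5, rounded up to 58.

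The protocol's 58 is therefore reproduced, giving 2 × 58 = 116 in total. The t-test version gives 58.5, so 59, which is close enough that the base figure is not in question.

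**Step 2. Find what gives 140.**

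- 116 × 1.2 = 139.2, rounded up to 140 (equally, 58 × 1.2 = 69.6, so 70 per group). This matches.
- 116 / 0.8 = 145 (by group, 58 / 0.8 = 72.5, so 73 per group and 146 in total). This does not match.

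**Step 3. Apply the stated drop-out to the stated total.** This does not depend on how 140 was reached.

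- 140 × 0.8 = 112, or 56 per group: 2 per group and 4 in total below the stated need.
- Largest loss that still leaves 116: (140 − 116)/140 = 24/140 = 17.1%.

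**Step 4. Effect on power**, for difference 5 and SD 9.57, with drop-outs contributing no data:

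| Evaluable per group | Normal approximation | t test |
|---|---|---|
| 58 | 80.3% | 79.7% |
| 56 | 78.9% | 78.2% |

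Read down one column at a time, the loss is about 1.4 percentage points by either method. Setting the t-test 78.2% against a nominal 80% would overstate it, because by the t test the planned 58 per group already gives 79.7% before any drop-out.

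**Step 5. The same effect on the scale of the outcome.** With 56 per group, the difference detectable with 80% power is (1.960 + 0.842) × 9.57 × √(2/56) ≈ 5.07 instead of 5. Equivalently, 80% power for a difference of 5 would be restored by an SD of 5 / [(1.960 + 0.842) × √(2/56)] ≈ 9.44 instead of 9.57, about 1.3% lower.

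**The case against.** The strongest reply is that the discrepancy is too small to matter. The SD comes from a single earlier study, the 20% is itself a planning guess, and a 1.3% change in the SD would cancel the shortfall. This stands, and it settles the weight of the point: it is minor.

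A second reply is that the 20% may have been meant as an addition to the 116 evaluable infants. That gives 23.2 extra, rounded to 24, and exactly 140. The protocol does not name the denominator, so this cannot be excluded. It is the weaker reading, because the text speaks of drop-out and its criteria concern infants already in the study. Even if it is right, the sentence needs rewording, since a reader will take 20% as a share of those enrolled. For the same reason, multiplication by 1.2 can be offered only as the calculation that matches, not as a documented step.

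A third reply concerns the power figures. They belong to one two-sample comparison of means, whereas the Statistical analysis section plans a repeated measures ANOVA on outcomes that include minute-by-minute readings. Power for that analysis depends on correlations that the protocol does not give. Nor does the protocol say that an infant who drops out part-way contributes no data. This also stands. A reader might infer that the trial as a whole misses 80% power, or that it must enrol more infants. The document does not support either inference; it supports only the statement that 58 per group is not retained under the protocol's own calculation.

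**Conclusion.** The sentence is wrong as written, and the error is minor. On the ordinary reading of drop-out as a share of those enrolled, with 1:1 allocation and equal losses, 140 infants less 20% leaves 56 per group against the stated 58. The total falls 5 short of the 145 that would keep 116, or 6 short of 146 with equal groups. The cost is about 1.4 points of power, conditional on the two-sample formula and on complete loss of data from infants who drop out. The base figure of 58 per group is sound. The mismatch between 140, 20% and 58 is certain on that reading; the multiplication by 1.2 remains an inference from the matching number.

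**What to change.** Keep 140 and replace the last sentence of the Sample size section with:

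> *140 infants allow for about 17% drop-out (24/140) while retaining 58 per group; at 20% drop-out 56 per group remain and power is about 79%.*

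It helps to add that the 79% is for the two-sample comparison by the normal approximation and assumes that drop-outs contribute no data.

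The cost is one sentence and a slightly less favourable stated figure. Recruitment, design and analysis do not change. Enrolling 146 would also make the figures agree, but a gap of this size does not justify the extra infants.

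### Two-week weight gain makes no provision for infants discharged well before day 14, and the named analysis would drop them; if discharge follows growth, a real difference is diluted

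*Protocol*

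**What the plan says.** Weight gain is one of three specific objectives in the Protocol (Objectives and Purpose): "To compare mean weight gain between premature infants exposed to mother's voice vs NICU environmental sound". No per-day or per-kilogram definition is given.

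The Inclusion and Exclusion Criteria select infants who are past the acute phase:
- Age: "All premature infants with corrected gestational age 27-35 weeks".
- Feeding: "Achieved full feeding of at least 120cc/kg/day".
- Not eligible: "Medically unstable infant: HIE, NEC, sepsis, on inotropic support", "Infant who is still on intravenous drip or parenteral nutrition", or mechanical ventilation.
- Infants must be in a closed incubator at entry.

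Under Study protocol, the course has a fixed length: "Intervention group will be exposed to total of 14 times (daily) prerecorded maternal voice within 2 week-period". Weighing covers the same period: "weight gain will be monitored every alternate day for 2 weeks using a standard weighing machine".

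The Dropout criteria have three entries: need for ventilation, need to be kept nil by mouth, and becoming medically unstable. Discharge of an infant is mentioned only in connection with a hearing test beforehand. Statistical analysis names repeated measures ANOVA in SPSS for the dependent variables; the t test and chi-square test are assigned to demographic data.

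**The concern.** The entry criteria favour infants who are progressing, while the exposure and the weight outcome need 14 more days of observation. An infant who goes home on day 9 because it is doing well meets no dropout criterion, yet has neither 14 sessions nor a two-week gain.

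If faster growers tend to go home sooner, the early leavers are not a random subset. Dropping them removes fast growers from both arms, and more of them from the arm that grows faster. Using their last weight credits them with fewer days of gain. Either way the weight comparison would understate a real benefit.

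**Working it through.** **1. What the protocol's figures give**

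- The sample size concerns physiological responses: n per group = 2 × (1.96 + 0.84)² × 9.57² / 5² ≈ 57.5, rounded up to 58, as stated.
- No difference or SD is given for weight, so a loss on weight gain cannot be turned into lost power from the protocol.
- Entry at 35 weeks plus 14 days puts the end of the course at 37 weeks. Entry at 27 weeks puts it at 29 weeks. Early discharge would therefore fall mainly on older entrants.
- No length of stay, discharge age or weight, or rule for leaving the incubator is given.

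**2. Direction of the bias**

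Let r be an infant's daily gain and G the gain at which it is discharged. It is observed for T = min(14, G/r) days, so its gain by last weight is r × T = min(14r, G).

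Take the extreme case in which every infant leaves at G = 250 g. At 25 g/day that is 250/25 = 10 days; at 27 g/day it is 250/27 = 9.3 days. Both arms show 250 g, a difference of 0 instead of (27 − 25) × 14 = 28 g. The rates still differ by 2 g/day.

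Because min(14r, G) never falls as r rises, this mechanism can shrink the difference in weight at exit but cannot reverse it, given the same distribution of G in both arms.

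**3. Size under assumed values**

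None of these inputs is in the protocol:
- r normal, mean 25 g/day (control) and 27 g/day (intervention), SD 6.
- G normal, SD 100 g, with the mean varied.
- True 14-day difference: 28 g.

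| Mean G | Leave before day 14, control v intervention | Difference, weight at exit | Difference, completers only |
|---|---|---|---|
| 500 g | 12.5% v 17.5% | 23.8 g | 23.9 g |
| 350 g | 50% v 58.5% | 12.9 g | 20.5 g |
| 250 g | 78% v 84% | 5.3 g | 18.8 g |

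If the last scheduled alternate-day weight is used in place of the weight at exit, the first two rows give about 22 g and 9.5 g. A per-day rate from the observed weights, multiplied by 14, gives about 28 g throughout.

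In the first row the difference retained is 22/28 = 79% to 24/28 = 86%. In the second it is 9.5/28 = 34% by last scheduled weight and 20.5/28 = 73% in completers.

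**The case against.** **Nothing shows that infants leave early.** This stands. A reader might infer that the healthiest infants do leave before day 14, or that the course cannot be delivered to part of the eligible population. The protocol supports neither. It gives no discharge data, entry starts at 27 weeks, and the closed-incubator criterion limits enrolment of infants nearest to going home.

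**Moving to a cot is not discharge.** This also stands. No passage makes leaving the incubator a reason to stop weighing. Only discharge necessarily ends in-unit weights.

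**The effect could be hidden or reversed.** A reader might reach this by imposing exit rates. Suppose leavers go at day 7 and gains are 25 and 27 g/day. With 20% v 10% leaving, the last-weight means are 0.8 × 378 + 0.2 × 189 = 340.2 g and 0.9 × 350 + 0.1 × 175 = 332.5 g, a difference of 7.7 g. With 30% v 10%, the intervention mean is 0.7 × 378 + 0.3 × 189 = 321.3 g and the difference is −11.2 g. Those gaps of 10 and 20 percentage points are assumed. When exit follows growth with a 2 g/day benefit, the gap was 5 to 8.5 points and the sign never changed.

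**Handling of incomplete weights belongs in a SAP.** This stands in part. A SAP may exist and is not shown, and the protocol nowhere specifies last minus first weight. But the fixed window, the deterioration-only dropout list and the named method are all in the protocol. Followed as written, with the standard complete-series form, they lose infants discharged well.

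**Scope.** The sample size rests on physiological responses. These and BIIP are measured within each session, so early discharge reduces the number of sessions but does not truncate the within-session changes. The 20% dropout allowance is also not expressly confined to deterioration.

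**Conclusion.** The point holds as a credible risk of unknown size to one of three specific objectives. The fixed two-week weight window has no provision for exit through recovery, and the named analysis in its standard form discards incomplete series. If discharge is linked to growth, the bias is toward no difference.

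At assumed exit of 12.5% v 17.5%, the loss is about 4 to 6 g of a true 28 g. It becomes large by last weight only when roughly half or more leave early, and the protocol gives no evidence of that. These figures rest on constant daily gain, the assumed means and SDs, and the same discharge threshold in both arms. Without a link between discharge and growth, this bias in the completer comparison does not arise.

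**What to change.** - Define weight gain as a rate (g/kg/day), with the reference weight for the denominator stated, estimated from all alternate-day weights from day 1 to day 14 or discharge, whichever comes first. A mixed model for serial weights would do this in place of complete-series repeated measures ANOVA.
- Keep infants who move to a cot or go home in the analysis with the weights they have.
- Record early discharge and leaving the incubator, and report sessions received and reasons for early exit by arm.

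The cost is protocol wording and a short exit record; the weights are already planned. The downside is that rates from short stays are noisier. An added entry criterion based on expected length of stay is not recommended: it relies on a prediction and narrows the population, and the rate definition removes the need for it.
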